14.3. Written Informed Consent and HIPAA Authorization

The PI at each research site will ensure that each patient is given full and adequate oral and written information about the nature, purpose, and possible risks and benefits of the study. Attention is directed to the basic elements that are required in the informed consent and process under US CFR for Protection of Human Subjects (21 CFR 50.25 and/or ICH E6 4.8.10). Patients must be told that they may withdraw from the study at any time. The patient should have ample opportunity to ask questions and should be allowed time to consider the information provided.

The patient's signed and dated informed consent must be obtained before any study procedures are conducted. Patients may require Care Partner support to be considered eligible for the study (e.g., needs help in physically completing assessments or requires assistance with transportation to clinic visits), but must be cognitively capable of communicating and providing responses to questions. Care Partners, if willing, may also need to sign the informed consent form indicating their willingness to assist the patient as necessary. Patients who refuse to participate or who withdraw from the study will be provided care and treated without prejudice.

The PI must maintain the original, signed, and dated ICF. A copy of the fully executed ICF must be given to the patient.

Each patient must also sign a HIPAA Authorization form before his/her participation in the study. A signed copy must be provided to the patient and a signed original shall be maintained in the patient's clinical file.

14.4. Investigator Obligations

The following is a list of key PI responsibilities during the study. A more detailed discussion of investigator obligations may be found in the US 21 CFR Part 50.

- The PI must ensure that the study is conducted according to the protocol as written and must protect the rights, safety, and welfare of study patients in their care. Only the Sponsor may modify the protocol. If a protocol amendment (and perhaps a new ICF) is needed, the Sponsor will prepare the documents and guide all investigators through the amendment process.
- The PI is required to maintain complete and accurate study documentation in compliance with current good documentation standards and make such documentation available as requested in the event of an inspection, review, or audit of the clinical research facility by the Sponsor, its representatives, and/or any appropriate regulatory agencies.
- In accordance with FDA reporting requirements, the PI and site personnel are required to collect, document, and report all SAEs and noteworthy AEs during the study and, under special circumstances, thereafter (as described in Section 9.4 and Section 11.4.2 of this protocol).

15. DATA MANAGEMENT

All data collected in the context of this study will be stored and evaluated in accordance with regulatory requirements and applicable guidance for electronic records.

15.1. Data Capture

Investigative sites will be provided secure access to a 21 CFR Part 11-compliant eCRF and eCOA system(s) for collecting patient data. All information recorded in the eCRF must be supported by source documentation in the patient's medical file unless the electronic entry is the original entry (e.g., assessments completed through electronic device). The patient's source file must include (but is not limited to) the following:

- An entry documenting that the patient signed and dated an ICF and HIPAA authorization form before entry into and participation in the study
- Patient study identification number and protocol number
- Medical diagnosis and entries for all treatment and medications
- Summaries of all clinic visits including those for study purposes
- Documentation of all SAEs and noteworthy AEs

15.2. Retention of Patient and Administrative Records

The Sponsor (or designee) will be allowed to conduct site visits to study facilities for the purpose of monitoring and auditing any aspect of the study. The PI must also allow the IRB and any applicable regulatory agency direct access to all study-related facilities and materials, including original source documents and/or certified copies of original records of clinical findings, observations, or other activities relevant to the study and necessary for the reconstruction and evaluation of study conduct.

The study site must provide the Sponsor with the following essential documents prior to study initiation and retain a copy in its study files:

- Current curriculum vitae for the PI
- Sponsor-approved protocol and protocol amendments signed and dated by the PI
- Written IRB approval of the protocol and protocol amendments
- IRB membership roster or assurance number
- ICF and HIPAA authorization form approved by the IRB and accepted by the Sponsor
- Fully executed Clinical Trial Agreement between the Sponsor and the site

In addition to the documents listed above, the site must also retain the following items:

- All original ICFs/HIPAA authorizations fully signed and dated
- All IRB approvals and correspondence (e.g. informed consent [including any approved revisions], protocol, AEs [including SAEs] advertisements, newsletters)

- Copies of all correspondence (emails, faxes, postal mail) pertaining to the study from the Sponsor and IRB and other relevant parties
- Copies of all safety-related information
- Study personnel signature and delegation of authority log for the site
- A separate file containing the Clinical Trial Agreement and related financial correspondence between the Sponsor and the site

The PI and/or study site must retain copies of all pertinent study information, essential documents, and study data records (e.g., eCRFs, eCOAs, original data, patient identification lists, etc.) for a minimum period of 2 years after the study database lock and closure or until notified, in writing, by the Sponsor that these documents/copies are not needed.

If record retention at the investigative site is no longer possible, or if the investigative site or study records are relocated, the Sponsor must be notified immediately in writing with the address of the new storage location.

16. CONFIDENTIAL INFORMATION

16.1. Confidentiality of Study Data

Confidential information refers to any information provided to your site by the Sponsor or its agents that has not been previously published. This includes, but is not limited to, the study protocol (and protocol amendments, if any), eCRFs (if applicable), assay methods, and basic scientific data. Any data collected at the site during the study are also considered confidential. All confidential information remains the sole property of the Sponsor, may not be disclosed to others without prior written consent from the Sponsor, and may not be used except in the performance of this study. The PI is required to provide the Sponsor with complete test results and all data obtained during this study. At the discretion of the Sponsor, the information from this study may be made available to any applicable regulatory agency and/or other physicians who are conducting similar studies.

16.2. Confidentiality of Patient Records

To maintain patient confidentiality, all laboratory results (if applicable), eCRFs (if applicable), reports, and other records will be coded using patient identification numbers. Only research staff and Sponsor officials will have access to the records. Patient information will not be released without written permission, except as necessary for monitoring by the Sponsor or a regulatory agency.

By participating in this protocol, the PI and research site agree that within local regulatory restrictions and ethical considerations, the Sponsor or any regulatory agency may consult and/or copy study documents to verify eCRF data.

Patient confidentiality will be maintained in any publications or presentations that result from this study.

17. PUBLICATION POLICY

The Sponsor recognizes the importance of communicating medical study data and therefore encourages publication of such data in reputable scientific journals and at seminars or conferences. The details of the processes of producing and reviewing reports, manuscripts, and presentations based on the data from this study are described in the Clinical Trial Agreement between the Sponsor and the PI or his/her institution.

## 1. LIST OF ABBREVIATIONS

**Table 1: List of Abbreviations**

Abbreviation	Term
AE	Adverse Event
ALT	Alanine Aminotransferase
ANCOVA	Analysis of Covariance
ANOVA	Analysis of Variance
CMH	Cochran Mantel-Haenszel
COSTART	Coding Symbols for Thesaurus of Adverse Reaction Terms
CRF	Case Report Form
CRO	Contract Research Organization
CSR	Clinical Study Report
DOB	Date of Birth
dy	Days
GCP	Good Clinical Practices
GGT	Gamma-Glutamyl Transferase
ICD-9	International Classification of Diseases – 9 th Edition
IRB	Institutional Review Board
ITT	Intent-to-Treat Population
LLN	Lower Limit of Normal
LOCF	Last Observation Carried Forward
MedDRA	Medical Dictionary for Regulatory Activities Terminology
mo	Months
N	Total Sample Size
NIMH	National Institute of Mental Health
OC	Observed Cases
OTC	Over the Counter Medication
PCS	Potential Clinical Significance
PP	Per-Protocol Population
S	Sex
s.d.	Standard Deviation

**Table 1: List of Abbreviations (Continued)**

Abbreviation	Term
SAE	Serious Adverse Event
SAS	Statistical Analysis System
SR	Sustained Release
TG	Treatment Group
TS	Transdermal Delivery System-Placebo
ULN	Upper Limit of Normal
VAS	Visual Analogue Scale
WBC	White Blood Cell Count
WHO	World Health Organization
yr	Years

## 2. INTRODUCTION

The purpose of this statistical analysis plan (SAP) is to describe the planned analyses and data displays to be included in the Clinical Study Report (CSR) for Protocol USWM-SA1-4001.

Protocol Revision Chronology:		
Protocol	28-AUG-2017	Original
Protocol	01-NOV-2017	Amendment 1
Protocol	12-OCT-2018	Amendment 2

This SAP was developed in accordance with ICH E9 guidelines. All decisions regarding final analysis, as defined in this SAP document, will be made prior to Database Freeze (unblinding) of the study data. Further information can be found in the protocol.

### **3. STUDY OBJECTIVES AND ENDPOINTS**

#### **3.1. Study Objectives**

The objective of this prospective, observational study is to gather real-world observational data from the following assessments in individuals in the United States (US) with Parkinson’s disease (PD) during XADAGO treatment: the Movement Disorders Society – Unified Parkinson’s Disease Rating Scale (MDS-UPDRS), the Parkinson’s Disease Questionnaire (PDQ-39), the Montreal Cognitive Assessment (MoCA), the Treatment Satisfaction Questionnaire for Medication (TSQM-9), the Clinical Global Impression of Change (CGI-C), and the Patient Global Impression of Change (PGI-C).

#### **3.2. Study Endpoints**

Study endpoints are the changes from the Baseline Visit to Visit 3 (Study Day 60, Primary Endpoint) in motor and non-motor symptoms, general health status/quality of life, treatment satisfaction, and global impression as measured by MDS-UPDRS, PDQ-39 and MoCA, TSQM-9, CGI-C and PGI-C, respectively.

## **4. STUDY DESIGN**

### **4.1. Summary of Study Design**

This is a multisite, prospective, observational study to evaluate clinician-reported outcomes (ClinROs) and patient-reported outcomes (PROs) related to motor and non-motor symptoms, health status/QoL, and treatment satisfaction in a “real world” PD population in the US newly prescribed XADAGO in accordance with the Package Insert indication. The decision to prescribe XADAGO by clinician and patient must be made before site study staff discuss the study with the patient. If the patient is interested in participating in the study, an informed consent form (ICF) will be provided to the patient for review, contents of the ICF will be discussed, and patient’s signature will be obtained. Enrolled patients will be prospectively followed for 2 months, with the potential to participate in a 4-month Extension Study.

The Schedule of Assessments ([Table 2](#)) presents all the study activities that will occur at each study interaction with patients during clinic visits, by telephone at protocol-specified time points, and by PRO via the electronic Clinical Outcome Assessment (eCOA) system. Investigative sites will be provided secure access to 21 CFR Part 11-compliant electronic Case Report Forms (eCRF), and sites and patients will have access to the eCOA system(s) for collecting all patient data.

### **4.2. Definition of Study Drugs**

The study drug that will be used in the trial is Safinamide.

### **4.3. Sample Size Considerations**

#### **4.3.1. Sample Size Justifications**

Since this is an observational study, sample size is determined based on clinical judgment. Up to 600 patients are planned for screening. This is expected to result in a final sample size of up to 540 eligible and evaluable enrolled patients, distributed among approximately 30 investigative sites in the US.

#### **4.3.2. Sample Size Re-estimation**

Not applicable.

### **4.4. Randomization**

This is not a randomized study.

### **4.5. Clinical Assessments**

**Table 2: Schedule of Assessments**

Protocol Activity (Visit Type, Location, and Number;                      Study Day and Month;                      Window Allowance)	2-Month Main Study			4-Month Extension Study		
	Screening/Baseline Assessment Visit a	Follow-up	Primary Endpoint Visit	Follow-up	PRO Assessment Only	Follow-up
	Clinic	Telephone	Clinic	Clinic		Clinic
	Visit 1	Visit 2	Visit 3	Visit 4	Visit 5	Visit 6
	Day 1	Day 30	Day 60	Day 90	Day 120	Day 180
	Month 1		Month 2	Month 3	Month 4	Month 6
	±7 days	±2 days	±7 days	±7 days	±7 days	±14days
Informed Consent and HIPAA Authorization	X					
Eligibility: Inclusion/Exclusion Criteria	X					
Medical History and Demographics	X					
Medical History of PD, other Neurological Conditions	X					
Presentation of Study Instructions to Patient	X					
Registration and Training on eCOA System	X					
Concomitant Medications Assessment b	X	X	X	X		X
XADAGO Administration Compliance Review b		X	X	X		X
PRO Compliance Review b			X	X		X
Adverse Events Assessment b			X	X		X
MDS-UPDRS b	X		X	X		X
PDQ-39 c	X		X	X		X
MoCA b	X		X			X
TSQM-9 c		X	X	X	X	X
CGI-C b			X	X		X
PGI-C c			X	X		X

a Screening will take place not more than 7 days before the Baseline Visit and may occur at the same time as the Baseline Visit. The first study dose of XADAGO will occur in the clinic on the Baseline Visit day, which will be designated Study Day 1.

b Assessments to be administered by the PI/certified or HCP designee.

c Assessments to be completed by the patient, with Care Partner assistance, if required.

## **5. PLANNED ANALYSES**

### **5.1. Interim Analyses**

Interim data analyses will be performed periodically to provide study updates and to support potential presentation of interim results

. Since this study is observational only and treatments are not assigned to specific patient/treatment groups, these interim analyses will have no statistical implications.

### **5.2. Final Analyses**

After the last enrolled subject completes Visit 3, the database will be locked. The final analyses will be performed after the database lock.

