11.4. Recording Adverse Events

AEs spontaneously reported by the patient and/or in response to an open question from the study personnel or revealed by observation will be recorded during the study at the investigational site.

Information about AEs (and SAEs) will be collected from the time the patient signs the informed consent for this study and takes the first study dose of XADAGO until the patient’s last follow-up visit. The AE term should be reported in standard medical terminology when possible. For each AE, the investigator will evaluate and report the onset date, resolution date, intensity, causality, action taken, serious outcome (if applicable), and whether or not it caused the patient to discontinue the study.

Intensity will be assessed according to the following scale:

- Mild (awareness of sign or symptom, but easily tolerated)
- Moderate (discomfort sufficient to cause interference with normal activities)
- Severe (incapacitating, with inability to perform normal activities)

It is important to distinguish between serious and severe AEs. Severity is a measure of intensity whereas seriousness is defined by the criteria under Section 11.2.2. An AE of severe intensity may not be considered serious.

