12. STATISTICAL METHODS

12.1. General Statistical Considerations

All assessments will be summarized at specified time points. Continuous variables will be summarized using the number of patients, mean, standard deviation (SD), and minimum, median, and maximum values. Categorical variables will be summarized using the number and percentage. All data will be summarized according to cohort and overall.

Endpoints are defined at Study Day 60 (primary endpoint). Descriptive statistics will be provided for all data collected. All tests of significance, unless otherwise stated, will be performed using a two-sided alpha at 0.05.

All analyses will be performed using SAS[®] Version 9.3 or higher (SAS Institute, Inc., Cary, North Carolina, USA).

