12.7. Population and Patient Disposition

Frequency of patients enrolled, safety population, and evaluable patients will be displayed. Populations will be reported by cohort, site.

Patient disposition will be summarized in each cohort along with reason of discontinuation. Frequency and percentages of patients completing and discontinuing the study prior to the primary endpoint (Study Day 60) and prior to the last study visit (Study Day 180) will be analyzed.

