## **6.4. Data Presentation Conventions**

Continuous variables (e.g. age) are summarized using descriptive statistics (the number of subjects with available data, the mean, standard deviation (SD), median and minimum and maximum). Categorical variables (e.g. race) are summarized using counts and percentages. Percentages are calculated using the total subjects in the XADAGO group.

The following conventions are applied to all data presentations and summaries.

- For continuous variables, all mean and median values are formatted to one more decimal place than the measured value. Standard deviation values are formatted to two more decimal places than the measured value. Minimum and maximum values are presented with the same number of decimal places as the measured value.
- For categorical variables, the number and percentage of responses are presented in the form XX (XX.X%) where the percentage is in the parentheses.
- Date variables are formatted as DDMMYY for presentation. Time is formatted in military time as HH:MM for presentation.
- Wherever possible, data will be decimal aligned.
- Unless otherwise stated, any statistical tests performed will use 2-sided tests at the 5% significance level.

The table and listing shells and table of contents as part of this SAP provide the expected layout and titles of the tables, listings and figures. Any changes to format, layout, titles, numbering, or any other minor deviation will not necessitate a revision to the SAP nor will it be considered a deviation from planned analyses. Only true differences in the analysis methods or data handling will necessitate such documentation. The appropriate listings supporting the tables will be included and are not specified in the individual sections throughout the document.

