## **6.8. Handling of Missing Data**

### **6.8.1. Missing Efficacy Endpoints**

The missing efficacy data will be imputed by Last-Observation-Carried-Forward (LOCF) method.

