## **7. STUDY POPULATION**

### **7.1. Subjects Disposition**

The disposition of all subjects will be summarized by cohort and site. Subject disposition tables will include the number and percent of subjects who were:

- included in each analysis populations (Safety, Evaluable);
- discontinued from the study early, summarized by primary reason for discontinuation.

The number of subjects screened and number of days in the study of each subject will also be summarized by cohort and overall.

Frequency and percentages of patients completing and discontinuing the study prior to the primary endpoint (Study Day 60) and prior to the last study visit (Study Day 180) will be analyzed by cohort and overall.

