### **9.1. Overall Summary of Tolerability**

The overall summary of tolerability table presents the data for all treated subjects by cohort and overall. Entries in this table are the number of:

1. Subjects treated and subject months of drug exposure by treatment (50 mg vs 100 mg).
2. Subjects with adverse events.
3. Adverse events.
4. Subjects with serious adverse events.
5. Subjects discontinuing due to adverse events.
6. Deaths.

The subject data listing provides a complete disclosure of adverse events as recorded in the CRF and supports this table and all other AE summary table subsets.

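### The SAP's only database lock is triggered at the last enrolled patient's Day 60, yet both documents require Day-180 disposition, and no later lock, cut-off or extension report is described

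*SAP*

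**What the plan says.** SAP 5.2 (Final Analyses) gives one lock and one trigger: "After the last enrolled subject completes Visit 3, the database will be locked. The final analyses will be performed after the database lock". The schedules in both documents place Visit 3 at Day 60 and Visit 6, the last extension visit, at Day 180.

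Several outputs reach beyond Day 60:

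- SAP 7.1 requires that completion and discontinuation "prior to the last study visit (Study Day 180) will be analyzed by cohort and overall". Protocol 12.7 has the same requirement ("prior to the last study visit (Study Day 180) will be analyzed"). SAP 7.1 also summarises each patient's days in the study.
- SAP 9.1 reports subject-months of drug exposure, and SAP 9.3 reports patients' status at the end of the study.
- Protocol 11.4 collects adverse events from when the patient signs consent and "takes the first study dose of XADAGO until the patient’s last follow-up visit".
- Protocol 12.1 promises: "Descriptive statistics will be provided for all data collected".

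The remaining references to timing do not add a later data cut. SAP 5.1 and Protocol 12.6 allow periodic interim analyses without dates or cut-offs. The SAP Introduction mentions a single undated freeze. Protocol 15.2 mentions a lock only to start the record-retention period.

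**The concern.** The only event that the SAP names as releasing the database comes about four months before the last enrollee could supply the Day-180 information that the same SAP lists as an output. The plan does not say which lock feeds the Day-180 disposition table, or what happens to extension data that accrue after the lock.

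At stake are the descriptive tables for the extension: Day-180 completion and discontinuation, exposure, and late adverse events. The patients affected are those enrolled last, so the final tables would cover the extension fully for early enrollees and partly for late ones. SAP 9.3 lists completers, premature discontinuations and reasons, but no category for patients still in follow-up. Such patients could therefore be placed in the wrong row.

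**Working it through.** There is no figure in the plan to reproduce; the check is date arithmetic.

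**Inputs.** Visit 3: Day 60 ±7, so Day 53 to 67. Visit 6: Day 180 ±14, so Day 166 to 194 (schedules in both documents; SAP 6.7.4). Planned enrolment: up to 540 (Protocol Synopsis). Planned calendar: first patient enrolled November 2017, last patient completed April 2020 (Protocol Synopsis). Extension uptake, accrual pace and dropout are not given.

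**Step 1: who has not reached Visit 6 at the trigger.** Take a patient enrolled *d* days before the last enrollee. When the last enrollee attends Visit 3 on that person's study day *v3*, the earlier patient is on study day *v3* + *d*. Visit 6 is still outstanding if *d* < *v6* − *v3*.

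- Nominal: 180 − 60 = 120 days.
- Shortest: 166 − 67 = 99 days.
- Longest: 194 − 53 = 141 days.

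**Step 2: length of accrual (assumption).** The calendar does not say whether completion means Day 60 or Day 180, so both are shown.

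- Completion = Day 180: last enrolment is 179 days before 1 to 30 April 2020, that is 5 October to 3 November 2019. Counted from 1 to 30 November 2017, accrual is 674 to 732 days.
- Completion = Day 60: last enrolment is 59 days before, that is 2 February to 2 March 2020. Accrual is 794 to 852 days.

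**Step 3: share affected.** Under uniform accrual, no dropout and every patient entering the extension, share = gap / accrual.

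| Case | Share | Of 540 |
|---|---|---|
| Lowest, 99/852 | 11.6% | 63 |
| Nominal, 120/852 | 14.1% | 76 |
| Nominal, 120/674 | 17.8% | 96 |
| Highest, 141/674 | 20.9% | 113 |

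The lowest and highest rows put every patient at the same window edge, so they bound the range and are not likely values.

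**Step 4: scale by extension uptake.** Patients outside the extension have no Visit 6.

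- 50% uptake: 0.5 × 540 × 99/852 = 31, to 0.5 × 540 × 141/674 = 56.
- 25% uptake: 0.25 × 540 × 99/852 = 16, to 0.25 × 540 × 141/674 = 28, about 3% to 5% of those enrolled.

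**Step 5: does another rule fill the gap?** SAP 6.8.1 says "The missing efficacy data will be imputed by Last-Observation-Carried-Forward (LOCF) method"; it is confined to efficacy data and does not supply disposition, exposure or adverse events. SAP 6.4 says "Percentages are calculated using the total subjects in the XADAGO group", so patients still in follow-up would stay in the denominator of a Day-180 percentage while being neither completers nor discontinuations.

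**The case against.** The strongest reply is that SAP 5.2 fixes only an earliest time. A lock taken after the last Visit 6 would satisfy SAP 5.2 and SAP 7.1 together. That stands: a reader might infer that the plan is bound to discard extension data, and the documents do not support that. What remains is that nothing makes the lock wait for Visit 6, and Visit 3 is the only trigger named.

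A second reply is that SAP 6.1 puts the data extraction date on every output, has tables state how many subjects the data apply to, and separates unknown from missing values. The table shells are not in the text available for review, so a row for ongoing patients cannot be ruled out. This would help a reader to interpret the tables, but it would label the missing follow-up without supplying it.

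Third, days in study and subject-months can be computed up to any lock date. This also stands: exposure and adverse event tables would be truncated for late extension patients, not impossible to produce. Likewise, the presence in the denominator of patients who never enter the extension has nothing to do with lock timing and would persist under a later lock.

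Fourth, endpoints are defined at Day 60 and SAP 8.4 analyses change to Day 60 only. A reader might infer that the primary analysis is at risk, but it is not to any material degree. A patient enrolled shortly before the last enrollee could have Visit 3 after that person's, but only by up to 67 − 53 = 14 days, with opposite window extremes and a lock on the trigger day. Recording and reporting of serious adverse events under Protocol 11.4.2 do not depend on the lock.

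Finally, the counts rest on uniform accrual through a redesign in October 2018 (Amendment 2) and on unknown uptake. They are illustrations; the point does not depend on them.

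**Conclusion.** The gap in the text is certain: one lock, a Day-60 trigger, Day-180 disposition required in both documents, and no later lock, cut-off or extension report. The data consequence is conditional on the lock being taken at its trigger. In that case, extension patients enrolled within about 120 days of the last enrollee lack Day-180 status in the final tables, and their exposure and adverse event data stop early. The size is at most 63 to 113 patients under the assumptions above, and it falls in proportion to uptake. This should be fixed before the lock. It affects descriptive extension outputs and does not threaten the Day-60 results.

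**What to change.** In SAP 5.2, tie the final lock to the last extension patient's Visit 6 or discontinuation, and take Day-180 disposition, exposure and the complete adverse event tables from that lock. Day-60 results can be reported earlier in either of two ways:

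- from a Main Study lock set once all enrolled patients have completed Visit 3 or discontinued; or
- under the interim analyses already allowed by SAP 5.1 and Protocol 12.6, keeping a single final lock.

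Any table made from the earlier cut should show patients still ongoing separately from premature discontinuations (SAP 7.1 and 9.3).

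Alternatively, state that this SAP covers the Main Study only, remove its Day-180 outputs, and name the document that will deliver the disposition required by Protocol 12.7.

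The cost is a few lines of SAP text plus a second data cut up to about four months after the first (sooner if the last enrollee does not enter the extension), or one lock that is later by the same amount. No visit, assessment or treatment changes.
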